### 2.3 Design & intervention

The study is designed to evaluate SMC effectiveness and consists of three interventional study arms, with the first arm receiving an intervention that is implemented as part of routine control.

Study arm 1:	SMC in children under the age of 5 years, implemented by the Ministry of Health (MoH) without directly observed treatment for the full course of SMC
Study arm 2:	SMC in children under the age of 5 years, with directly observed treatment for the full course of SMC
Study arm 3:	SMC in children under the age of 10 years, with directly observed treatment for the full course of SMC

SMC consists of SP and AQ administered daily for three days. SP is given on the first SMC day only while AQ is given daily over three days. In total 4 rounds of SMC will be conducted during the peak malaria transmission season from July to October, separated by approx. 30 days.

Each study arm contains 62 clusters; each cluster consists of 3 compounds where each compound has at least one child aged 3-59 months and one child aged 5-9 years. (186 compounds per arm; 558 compounds in total). Differences in SMC coverage and efficacy will be determined in the SMC-targeted age groups. In contrast, all age groups will take part in the evaluation of the study to assess the impact of the intervention on the infectious reservoir in the community and compare parasite carriage in targeted and untargeted populations. To detect possible behavioural contamination and differences in SMC uptake or adherence in study arm 1 compared to what would be observed if there would be no

study team present, a single cross-sectional survey 7 days after the last (4th) round of SMC coverage is assessed outside the study area (2-5 kilometres from the nearest enrolled study compound) by questionnaire and samples to determine plasma levels of SMC drugs and parasite carriage by qPCR. Plasma levels of SMCR drugs are used as the most definitive evidence of differences in SMC uptake/adherence.

Scheduled surveys and scheduled or unscheduled sampling timepoints will take place in each arm; these surveys are designed and timed for several outcome measures and include:

- i) a survey prior to first SMC roll-out (performed in all compounds).
- ii) mid-study surveys 3, 4 and 5 weeks after the last SMC roll out (each compound will participate in one of these surveys).
- iii) end-of-study survey up to 10 weeks after last SMC roll out (performed in all compounds).

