### **4 Study objectives**

The specific study objectives are to:

- i) compare SMC effectiveness in children aged 3-59 months as implemented by the national malaria control program and SMC implemented in a research context where all doses are directly observed.
- ii) Evaluate the effectiveness of SMC to reduce malaria infection prevalence in 5-9 year olds

- iii) quantify the infectious reservoir and the contribution of different age groups to transmission with conventional SMC (<5 years) and extended SMC (<10 years)
- iv) determine the impact of drug resistance (by molecular typing of *dhps*, *dhfr*, *pf crt* and *pfmdr1*) and drug absorption on SMC efficacy
- v) understand social barriers and enablers interfering with SMC efficacy and how SMC uptake is related to health equity with special attention to gender inequalities.
- vi) quantify SMC efficacy decay under programmatic conditions and key drivers of this decay.

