For assessments of the human infectious reservoir, the intervention study is too large in scope (i.e. 558 compounds, compared to 180 in the previous INDIE project) and the time-window for transmission assays is too narrow (i.e. transmission assays are ideally done within weeks after SCM administration) to assess a direct impact of SMC on gametocyte infectivity with a conventionally powered comparison between arms. Thus a combination of methodologies (quantification of the association between gametocyte density and infectivity in the absence of treatment; imputed mosquito transmission from gametocyte density) are used (i, ii) It was further shown that direct comparisons of the association between gametocyte density and mosquito infection rates in mosquito feeding assays can demonstrate whether imputation is indeed acceptable across populations (i) or whether there are subpopulations with a different association (for example due to gametocyte-sterilizing effects of antimalarials (iii)). These insights will be used to perform mosquito feeding assays on gametocyte positive individuals with and without prior SMC and compare mosquito infection rates for a given gametocyte density (iii). Since the hypothesis is that SPAQ will permanently sterilize gametocytes, any reduced infectivity of gametocytes will remain apparent even after drug levels have waned (i.e. the gametocytes are permanently damaged by drug exposure) (iv). A possible sterilizing effect of SPAQ can be assessed by preferentially recruiting children who are gametocyte positive at the start of SMC and invite them for mosquito feeding post SMC. This will be done in children aged 5-9 years only who carry the highest parasite densities and highest gametocyte prevalence/density (i); this also avoids phlebotomy from the youngest children. A median gametocyte density of ~14 gametocytes/ $\mu$ L (IQR 1.8-44.2) as previously observed post-SMC (v, vi) is anticipated. Whilst the exact number of experiments that can be conducted will be dictated by mosquito husbandry, simulations indicate that when recruiting 100 children who received SPAQ (arm 3) and 100 children who did not (arms 1 & 2) and dissecting 40 mosquitoes per experiment, we would have >90% power to detect a 70% reduction in infectivity (vii).

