single modelled association will be used. If drug levels do have a statistically significant impact on transmission potential, all estimates of the infectious reservoir within one month of SMC will take study arm into account. For the infectious reservoir at the final end of study survey, no impact of SMC drugs on transmission efficiency is assumed. The contribution of different age groups (younger than 5 years, 5–15 years, 16 years and older) to the infectious reservoir will be estimated using all data (including parasite-negative observations where zero transmission is assumed)

14. *Prevalence of drug resistance markers in infected children aged 3 months-9 years assessed post each round of SMC (between arm comparison) [during the entire study].*
15. *Description of perceived social barriers to SMC uptake [during the entire study].*
16. *Quantification of SMC efficacy decay under programmatic conditions [during the entire study].*

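### The infectious-reservoir estimate (exploratory endpoint 13) applies a drug effect by study arm although treatment follows age within arm, and its 5-15 year band straddles the age-10 limit of extended SMC

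*SAP*

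**What the plan says.** Objective iii (SAP section 4) is to quantify the reservoir and the "contribution of different age groups to transmission with conventional SMC (<5 years) and extended SMC (<10 years". Section 2.3 sets treatment by age within arm. Arm 2 is "SMC in children under the age of 5 years, with directly observed treatment for the full course of SMC"; arm 1 has the same age limit under programmatic delivery. Arm 3 is "SMC in children under the age of 10 years, with directly observed treatment for the full course of SMC". Nobody aged 10 or over is targeted in any arm, but all ages are evaluated.

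On the mosquito feeds, section 7 says "This will be done in children aged 5-9 years only". The planned contrast is 100 treated children (arm 3) against 100 untreated children (arms 1 and 2).

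In section 10.7, endpoint 12 relates infectivity to gametocyte density according to whether each participant has detectable AQ/DEAQ. Endpoint 13 then imputes the reservoir from gametocyte density. If drug levels show no effect, one curve serves everyone. The alternative reads "If drug levels do have a statistically significant impact on transmission potential", in which case "all estimates of the infectious reservoir within one month of SMC will take study arm into account". At the end-of-study survey no drug effect on transmission efficiency is assumed. The age breakdown is fixed as "The contribution of different age groups (younger than 5 years, 5–15 years, 16 years and older) to the infectious reservoir will be estimated using all" the data, parasite-negative observations included.

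**The concern.** Endpoint 12 estimates the drug effect by individual drug status. Endpoint 13 applies it by arm, and no rule converts one into the other. Among 5-9-year-olds, the only age group with feeds, arm and treatment coincide: arm 3 is treated, arms 1 and 2 are not. At other ages they do not coincide. Under-5s are treated in all three arms, and people aged 10 and over in none. An arm-specific curve learned from 5-9-year-olds and carried to other ages therefore puts the wrong curve on two groups, and both errors make arm 3 look better.

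The age bands raise a second, independent problem. The extension adds 5-9-year-olds, but the planned table reports them together with 10-15-year-olds, whom no arm targets. Both problems bear on objective iii, which asks how the size and age profile of the reservoir differ between conventional and extended SMC.

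**Working it through.** The SAP gives no reservoir figure to reproduce, so what follows sizes the problem under stated assumptions.

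**Inputs.** From the SAP: treated ages by arm (section 2.3), and a 70% reduction in infectivity as the planning effect (section 7), so treated people have relative infectivity 0.3. Assumed: gametocyte density equal across arms, which isolates the infectivity term, and untreated reservoir shares *u* (under 5), *s* (5-9) and *o* (10 and over), varied below.

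**Formulas.**
- By treated age: arm 2 = 0.3*u* + *s* + *o*; arm 3 = 0.3*u* + 0.3*s* + *o*.
- By arm, read literally: arm 2 = *u* + *s* + *o*; arm 3 = 0.3(*u* + *s* + *o*). The ratio is 0.30 whatever the shares.

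**All ages sampled within a month of SMC.**

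| Shares *u/s/o* (%) | Arm 2 by treated age | Arm 3 by treated age | Ratio | Literal arm rule |
|---|---|---|---|---|
| 20/30/50 | 0.060 + 0.30 + 0.50 = 0.860 | 0.060 + 0.090 + 0.50 = 0.650 | 0.76 | 0.30 |
| 15/45/40 | 0.045 + 0.45 + 0.40 = 0.895 | 0.045 + 0.135 + 0.40 = 0.580 | 0.65 | 0.30 |
| 25/50/25 | 0.075 + 0.50 + 0.25 = 0.825 | 0.075 + 0.150 + 0.25 = 0.475 | 0.58 | 0.30 |

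**Only under-10s sampled in that window** (drop *o*; only the under-5 error remains).

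| Shares *u/s* (%) | Arm 2 by treated age | Arm 3 by treated age | Ratio | Literal arm rule |
|---|---|---|---|---|
| 20/30 | 0.360 | 0.150 | 0.42 | 0.30 |
| 15/45 | 0.495 | 0.180 | 0.36 | 0.30 |
| 25/50 | 0.575 | 0.225 | 0.39 | 0.30 |

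**Age profile.** With shares 20/30/50, people aged 10 and over make up 0.50/0.65 = 77% of the arm 3 reservoir, but 50% under the literal rule. Under-5s make up 0.06/0.86 = 7% of the arm 2 reservoir, but 20% under the literal rule.

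**Age band.** Let *f* be the share of the 5-15 band's infectivity carried by 5-9-year-olds. A 70% fall in 5-9-year-olds appears as a fall of 0.70*f* in the band: 28% at *f* = 0.4 and 49% at *f* = 0.7 (*f* assumed). This does not depend on the arm rule and applies at any timepoint.

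**The case against.** The strongest reply is that taking arm into account is a loose phrase. It does not prescribe one curve per arm for all ages. Endpoint 12 works with individual drug detectability, and section 10.7 elsewhere fixes age at round 1 because age determined the intervention. A careful analyst could bring in age or drug status. That stands: the bias belongs to the literal reading, and what the SAP does is leave the choice open.

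The reach is also limited. The rule needs a significant drug effect and covers only estimates within one month of SMC. In that window the listed gametocyte endpoint (weeks 3, 4 and 5 after the last round) is confined to SMC-targeted ages, whereas all-age gametocyte prevalence is listed only at end of study. Section 2.3 and endpoint 13 leave room for wider sampling without fixing it. If people aged 10 and over are not sampled, the distortion is the smaller one in the second table.

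Arm also carries real information. Section 7 expects fewer than half of arm 1 children to adhere fully and more than 20% to take no dose, so classing every targeted child as exposed would also be wrong. This stands and shapes the fix.

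A reader might infer that the significance condition adds to the tilt towards arm 3. It works the other way: a real effect that misses significance leads to one pooled curve, which understates arm 3's benefit. Nor does power stated for a 70% reduction mean that every smaller effect would be missed.

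**Conclusion.** The point holds as a fault of specification in an exploratory endpoint. Read literally, the arm rule credits arm 3 with too much. Under a 70% reduction, equal gametocyte densities and the assumed shares, it gives 0.30 where indexing by treated age gives about 0.58-0.76, or about 0.36-0.42 if only under-10s are sampled. The direction follows from who is treated and does not depend on the shares; the size does. These ratios describe the infectivity term alone. They are not forecasts of the full arm 3 / arm 2 reservoir ratio, which also depends on measured gametocyte density.

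The age-band point is separate and unconditional: the pre-specified 5-15 band dilutes the contrast that objective iii asks for.

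Two stronger readings are not supported. One is that the arm 3 benefit will be biased: the wording permits that but does not compel it, and the end-of-study reservoir is outside the rule. The other is that the 5-9 group cannot be isolated: individual age is held, and infection and gametocyte carriage in 5-9-year-olds are already compared between arms 2 and 3 under endpoints 1 and 9. The primary and secondary comparisons are unaffected.

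**What to change.** In endpoint 13, replace the instruction to take study arm into account with wording such as: *will use the gametocyte-infectivity association for exposed or unexposed individuals according to individual AQ/DEAQ status where measured, and otherwise according to SMC receipt, or arm and age at round 1 (with imperfect adherence in arm 1 allowed for)*. The fallback is needed because section 7 sets minimum numbers for plasma levels and allows selective sampling, so drug status may not be known for everyone.

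Report the reservoir in four age bands: under 5, 5-9, 10-15, and 16 years or older.

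This is a change of SAP wording. Arm and age at round 1 are already held and no new data are needed. The cost is slightly wider intervals in the finer bands.

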## 11 Conduct of analyses

### 11.1 Programming

Analysis will be performed using STATA software and R. Pharmacokinetic model evaluation and adherence simulations will be performed using NONMEM 7.5 with Pirana 2.9.9 as interface.

## 12 Reporting

Ethics committees at LSHTM and in Burkina Faso will receive annual reports on study progress. Final results will be uploaded to clinicaltrials.gov upon publishing of these results in a peer-reviewed journal.

## 13 Document history

Version	Author	Description of change	Date
1.0	[name]	New document	30 OCT 2023
2.0	[name]	Update secondary endpoint	29 JUL 2024

